6.3 During treatment

The following need to be performed on day 1 of each treatment cycle or within 72 hours before:

- ◆ Clinical examination (WHO PS, blood pressure, pulse rate, body weight, and body temperature).
- ◆ Assessment of all adverse events that have occurred since the previous visit and ongoing events from previous cycles should be followed.
- ◆ Complete blood counts to include hemoglobin, white blood cells, neutrophils, lymphocytes, platelets. For the experimental arm only, additional monitoring of hematological values should occur weekly during the first two cycles of therapy, and at least once between treatments in subsequent cycles
- ◆ A serum chemistry assessment to include at least creatinine, total bilirubin, ALT, AST, ALP, CPK, albumin, LDH, sodium, potassium, glucose, calcium. For the experimental arm only, additional monitoring of serum chemistry values should occur weekly during the first two cycles of therapy, and at least once between treatments in subsequent cycles
 - ◆ If ALP > 2.5 ULN, ALP hepatic isoenzyme 5-nucleotidase and/or GGT tests must be performed; ALP hepatic isoenzyme or 5-nucleotidase and/or GGT must be within the normal range.
 - ◆ Creatinine clearance will be calculated by Cockcroft and Gault formula (see Appendix E)
 - ◆ For the serum chemistry parameters not collected on the Serum Chemistry form: in case of abnormal value please record it as adverse event on the Adverse Event forms (grade, relationship, seriousness).
- ◆ Cranial MRI every 9 weeks from randomization and if clinically indicated
- ◆ Recording of corticosteroid dose every 9 weeks
- ◆ CT thorax/abdomen only if clinically indicated; if tumorous or unclear lesions detected repeat CT every 9 weeks and if clinically indicated
- ◆ HRQoL: QLQ-C30 (v3) and the BN-20 questionnaire: regardless the treatment arm, at week 3, week 6 and week 12 after treatment start (for more information see chapter 10).
- ◆ Pregnancy test (every two cycles)

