5.7.1.2 Permitted medications

- ◆ The use of growth factors is permitted

6 Clinical evaluation, laboratory tests and follow-up

The schedule of evaluation as described below applies to both treatment arms. A treatment cycle is defined as 3 weeks in the experimental arm and 3 or 4 weeks in the control arm, whatever is more appropriate for the selected treatment. Disease evaluation (MRI and/or CT) should follow exactly the schedule described below, irrespective of the treatment arm.

Treatment should start within an acceptable delay from randomization. A maximum delay of 21 days is accepted.

6.1 Within 4 weeks prior to randomization and within 4 weeks prior to treatment start

All evaluations performed more than 28 days prior to treatment start must be repeated.

- ◆ Informed consent
- ◆ Medical history and demographics (age, gender, medical conditions at entry)
- ◆ Clinical examination (including WHO performance status, neurological examination, blood pressure, pulse rate, body weight, height and body temperature)
- ◆ Recording of corticosteroid dose
- ◆ Assessment of all adverse events
- ◆ Cardiac monitoring: 12-lead ECG, LVEF (MUGA or echo)
- ◆ Complete blood counts will be performed, to include hemoglobin, white blood cells, neutrophils, lymphocytes, platelets.
- ◆ A serum chemistry assessment to include at least creatinine, total bilirubin, ALT, AST, alkaline phosphatase (ALP), CPK, albumin, LDH, sodium, potassium, glucose, calcium, hepatic isoenzymes 5-nucleotidase (if applicable), GGT (if applicable).
 - ◆ Alkaline phosphatase $\leq 2.5 \times$ ULN; if alkaline phosphatase $> 2.5 \times$ ULN, ALP hepatic isoenzyme and/or 5-nucleotidase and/or gamma glutamyltransferase (GGT) must be within the normal range. Creatinine clearance will be calculated by Cockcroft and Gault formula (see Appendix E)
 - ◆ For the serum chemistry parameters not collected on the Serum Chemistry form: in case of abnormal value please record it as adverse event on the Adverse Event forms (grade, relationship, seriousness).
- ◆ A serum pregnancy test is required in women of reproductive potential within 72 hours prior to randomization (and also within 72 hours prior to treatment start). The pregnancy test is to be repeated during protocol treatment every two treatment cycles.
- ◆ HRQoL: QLQ-C30 (v3) and the BN-20 questionnaire (for more information see chapter 10).

6.2 Within 2 weeks prior to randomization and within 4 weeks prior to treatment start

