6.5 Summary table

	Within 4 weeks prior to randomization ⁷	Within 2 weeks prior to randomization	During treatment		After treatment		
			On day 1 of each cycle or within 72 hours before	Every 9 weeks	End of treatment (30 days after last treatment administration)	Until PD every 9 weeks	After PD, every 9 weeks for the first year from randomization and every 12 weeks thereafter
Informed consent	♦						
Clinical examination	♦		♦		♦	♦ ⁸	
Medical history, demographics	♦						
Recording of corticosteroid dose	♦			♦		♦	
Adverse events assessment	♦		♦		♦	♦	
ECG	♦						
LVEF	♦						
Hematology ³	♦		♦		♦		
Serum chemistry ⁴	♦		♦		♦		
Pregnancy test	♦ ¹		♦ ¹		♦ ²		
Quality of life questionnaire (QLQ-C30 and BN20)	♦		♦ ⁵				
Tumor evaluation using cranial MRI		♦ ¹⁰		♦		♦ ⁹	
CT torax/abdomen		♣		♣ ⁶		♣ ⁶	
Survival						♦	♦

♦ mandatory

♣ if clinically relevant

1. Perform only in women of childbearing potential. The pregnancy test has to be done within 72h prior to randomization and also within 72 hours prior to treatment start and repeated during protocol treatment every two treatment cycles.

2. Pregnancy test must be repeated at 30 days and 3 months after last treatment dose.

3. Hematology test includes white blood cells, neutrophils, lymphocytes, platelets, hemoglobin counts.

Note for the experimental arm only: additional monitoring of hematological values should occur weekly during the first two cycles of therapy, and at least once between treatments in subsequent cycles.

4. Serum chemistry includes at least creatinine, total bilirubin, ALT, AST, ALP, CPK, albumin, LDH,

sodium, potassium, glucose, calcium. If alkaline phosphatase > 2.5 ULN, ALP hepatic isoenzyme and/or 5-nucleotidase and/or gamma glutamyltransferase (GGT) must be performed. Note: for the experimental arm only, additional monitoring of biochemical parameters (ALP, total bilirubin, CPK, and aminotransferases [AST and ALT]) should occur weekly during the first two cycles of therapy, and at least once between treatments in subsequent cycles.

5. QLQ-C30 (v3) and BN-20: at end of week 3/end of cycle 1, end of week 6/end of cycle 2, end of week 12/end of cycle 4 after treatment start, and at month 6 after treatment start regardless of treatment arm or progression status.

6. Only in patients with known tumorous or unclear lesions on prior CT

7. All evaluations performed more than 28 days prior to treatment start must be repeated

8. Only WHO PS

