8.2.3.4.1 Hematological parameters

The worst value of each hematological category will be identified and graded for each patient. Frequencies and percentages of each category will be tabulated per arm. A table with grade 3/4 frequencies and percentages will be provided.

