8.2.3.4.2 Biochemical parameters

The worst value of each biochemical category will be identified and graded for each patient. Frequencies and percentages of each category will be tabulated. A table with grade 3/4 frequencies and percentages will be provided.

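### Laboratory toxicity is tabulated as each patient's worst value, but trabectedin patients are sampled more often by design, so the two arms' rates are not comparable

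*Combined protocol and SAP*

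**What the plan says.** **Sampling.** In section 6.3 the common schedule is tied to the cycle: "The following need to be performed on day 1 of each treatment cycle or within 72 hours before". Trabectedin patients then have more. For blood counts: "For the experimental arm only, additional monitoring of hematological values should occur weekly during the first two cycles of therapy". For chemistry: "For the experimental arm only, additional monitoring of serum chemistry values should occur weekly during the first two cycles of therapy". From cycle 3 the extra draws continue, "at least once between treatments in subsequent cycles". The opening of chapter 6 lets control cycles run longer: "A treatment cycle is defined as 3 weeks in the experimental arm and 3 or 4 weeks in the control arm".

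The footnotes to the summary table (section 6.5) repeat the asymmetry. For chemistry they give a shorter list than section 6.3: "additional monitoring of biochemical parameters (ALP, total bilirubin, CPK, and aminotransferases [AST and ALT]) should occur weekly during the first two cycles of therapy".

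**Analysis.** Section 8.2.3.4.1 says "The worst value of each hematological category will be identified and graded for each patient", tabulated by arm with a grade 3/4 table. Section 8.2.3.4.2 says "The worst value of each biochemical category will be identified and graded for each patient"; it does not repeat that the table is by arm, but this is implied. Section 8.2.3.4 covers the whole study duration and rules out any formal comparison, p-value or confidence interval. Section 8.2.4 plans no sensitivity analysis. No section limits the tables to common time points or accounts for the number of samples.

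**The concern.** A worst value can only stay the same or get worse as draws are added, so the rate of grade 3/4 values depends on sampling as well as on toxicity. Here sampling differs by arm, by design and always in the same direction.

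Safety is a secondary endpoint (section 2.2). It is reviewed with efficacy at the futility look (section 8.3), and the introduction to chapter 10 says a PFS gain has to be weighed against the burden of treatment. The side-by-side percentages are the whole laboratory safety result, so a sampling artefact in them counts against trabectedin in that weighing.

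**Working it through.** The plan gives no figure to reproduce here. The check counts scheduled draws, then asks what the worst-value tables would show if toxicity were identical in both arms.

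**1. Scheduled draws after the first dose** (sections 6.3 and opening of chapter 6; patient still on treatment, no delays, one between-treatment draw per cycle from cycle 3, cycle 1 day 1 excluded as pre-dose).

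- Trabectedin: weeks 1, 2, 3, 4, 5, 6, then 7.5, 9, 10.5, 12.
- Control, 3-week cycles: weeks 3, 6, 9, 12.
- Control, 4-week cycles: weeks 4, 8, 12.

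| By week | Trabectedin | Control, 3-week | Control, 4-week |
|---|---|---|---|
| 6 | 6 | 2 | 1 |
| 12 | 10 | 4 | 3 |
| 26 | 19 | 8 | 6 |

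**2. Independent draws.** With risk p of an abnormal value at each draw, the chance of at least one in n draws is 1 − (1 − p)^n. At p = 5% by week 12:

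- 1 − 0.95^10 = 40.1%
- 1 − 0.95^4 = 18.5%
- 1 − 0.95^3 = 14.3%

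**3. Correlated draws.** Repeated values in one patient are correlated, so step 2 is an upper case. Let each draw be √ρ·b + √(1 − ρ)·e, with b a standard normal patient effect and e standard normal noise, abnormal when it exceeds the normal quantile for 1 − p. Simulation of 400,000 patients gives, as trabectedin / 3-week control / 4-week control:

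| p = 5% | ρ = 0.5 | ρ = 0.8 |
|---|---|---|
| By week 6 | 18.6 / 8.7 / 4.9% | 12.6 / 7.5 / 5.0% |
| By week 12 | 24.7 / 14.4 / 11.8% | 15.2 / 10.6 / 9.2% |

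Over p = 2%, 5%, 10% and ρ = 0, 0.5, 0.8, the week-12 results run from 7.2 / 4.6 / 4.0% (p = 2%, ρ = 0.8) to 65.1 / 34.4 / 27.1% (p = 10%, independent). Against a 3-week control the ratio lies between about 1.4 and 2.9 across weeks 6 and 12. The direction never changes. The values of p and ρ are assumptions; the documents give neither.

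**4. Would restricting to day 1 of each cycle repair it?** Not by itself.

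- *Number of draws.* By week 12 it gives 4 against 4 with a 3-week control (14.4% each at p = 5%, ρ = 0.5), but 4 against 3 with a 4-week control (14.4% against 11.8%).
- *Selection.* Section 5.6.1.2 requires trabectedin patients to meet laboratory thresholds (neutrophils, platelets, bilirubin, transaminases, CPK and others) before the next infusion. No equivalent is stated for control. Values on actual trabectedin dosing days are therefore selected to be near normal.
- *Time on treatment.* Section 8.1.1 assumes exponential PFS with 35% and 15% progression-free at 6 months. Medians are 6·ln 2/(−ln 0.35) = 4.0 months and 6·ln 2/(−ln 0.15) = 2.2 months. If treatment runs to progression, trabectedin patients accumulate more cycles and more day-1 draws.

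**5. Common calendar windows.** Over 12 weeks, three 4-week windows each hold at least one scheduled cycle-start assessment under all three schedules. Taking one per window gives 3 draws each, and 11.8% in each arm at p = 5%, ρ = 0.5.

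**The case against.** The strongest defence is that these tables are descriptive. Section 8.2.3.4 excludes formal comparison, and the protocol summary states the aim as collecting activity, safety and quality-of-life data on trabectedin, for which the worst value over all draws is suitable. That justifies keeping the table. It does not make the two columns comparable, and a reader will compare them.

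Two stronger readings are tempting and are not supported.

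- *A reader might infer that any laboratory difference comes from sampling alone.* Section 1.2 lists myelosuppression and transaminase elevations as known trabectedin effects, so part of a difference should be real.
- *A reader might infer that mid-cycle abnormalities in controls are lost altogether.* Section 6.3 asks both arms for all adverse events since the last visit, section 7.2.1 records the worst grade per cycle, and section 15.1 makes a laboratory finding an adverse event if, among other criteria, it causes significant symptoms or changes dosing. Sites may also draw extra samples, though none are required. What can be missed is the asymptomatic mid-cycle abnormality.

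On size, independent draws with 6 against 2 samples give 26% against 10% at p = 5% and 47% against 19% at p = 10%. The arithmetic is right, but these should not be read as the expected bias: correlation shrinks the gap. In the other direction, the model holds risk constant within the cycle; if abnormalities peak mid-cycle, when controls have no scheduled draw, the gap could be larger.

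**Conclusion.** The point holds as a matter of presentation and interpretation. The laboratory worst-value tables combine drug effect with sampling intensity, and under equal toxicity they would favour control. At p = 5% and correlation 0.5 to 0.8, the artefact by week 12 is about 5 to 10 percentage points against a 3-week control (15.2 − 10.6 = 4.6; 24.7 − 14.4 = 10.3) and 6 to 13 against a 4-week control (15.2 − 9.2 = 6.0; 24.7 − 11.8 = 12.9). These sizes rest on assumed values; the direction does not.

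The primary PFS analysis is unaffected. The documents do not support saying how much of an eventual difference is artefact. Nor do they support treating a table of dosing-day values as unbiased: for the gated parameters it could err in trabectedin's favour.

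**What to change.** Laboratory monitoring stays as it is. In sections 8.2.3.4.1 and 8.2.3.4.2:

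1. Keep the all-draws worst-grade tables, and label them as not comparable between arms because sampling differs by design. State that the biochemistry table is also by arm.
2. Report by arm the number of laboratory samples per patient and the time on treatment.
3. Add a supportive table by arm over one fixed calendar period from treatment start, for example the first 12 weeks, using one assessment per common window (for example three 4-week windows). Choose the assessment by its due date, not by the actual dosing day, so that pre-dose checks that fail the re-treatment criteria are counted. Give the number of patients assessed in each window, since patients leave treatment at different rates.
4. State that the supportive table misses mid-cycle nadirs and may understate trabectedin toxicity, so the two tables are read together.

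Sections 6.3 and 6.5 (footnote 4) should also be reconciled on which chemistry tests are added, because that decides which parameters carry the asymmetry.

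The cost is one extra set of descriptive tables. It requires dated individual laboratory values in the database, which the sponsor should confirm.

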6.3.1 Disease evaluation

- ◆ The disease will be assessed every 9 weeks by cranial MRI, regardless of interruptions and delays in therapy.
 - ◆ All organs that were found to be involved at the initial assessment will be re-investigated by the same method.
 - ◆ All lesions chosen as target during the initial assessment will be measured by the same method and, if possible, by the same person;
 - ◆ All investigations will be consistent with baseline in order that the development of new lesions in previously normal areas can also be determined.

6.4 After the end of treatment (Follow-up)

6.4.1 30 days after last administration of study drug

- ◆ Clinical examination (WHO performance status, blood pressure, pulse rate, body weight and body temperature)
- ◆ All ongoing adverse events from previous cycles should be followed until their resolution or stabilization or until the start of new anticancer therapy.
- ◆ Pregnancy test
- ◆ Complete blood counts to include hemoglobin, white blood cells, neutrophils, lymphocytes, platelets.
- ◆ A serum chemistry assessment to include at least creatinine, total bilirubin, ALT, AST, ALP, GGT, CPK, albumin, LDH, sodium, potassium, glucose, calcium.
 - ◆ If alkaline phosphatase > 2.5 ULN, hepatic isoenzymes 5-nucleotidase or GGT determinations must be performed; hepatic isoenzymes 5-nucleotidase and/or GGT must be within the normal range.
 - ◆ Creatinine clearance will be calculated by Cockcroft and Gault formula (see Appendix E)
 - ◆ Only the following parameters will be collected on the serum biochemistry form: creatinine, total bilirubin, ALT, AST, ALP hepatic isoenzymes 5-nucleotidase (if applicable), GGT (if applicable), CPK.
 - ◆ For the serum chemistry parameters not collected on the Serum Chemistry form: in case of abnormal value please record it as adverse event on the Adverse Event forms (grade, relationship, seriousness).

6.4.2 3 months after last administration of study drug

- ◆ Pregnancy test

6.4.3 Until PD or start of new anticancer therapy

- ◆ Cranial MRI every 9 weeks and if clinically indicated
- ◆ Recording of corticosteroid dose every 9 weeks
- ◆ CT thorax/abdomen only if clinically indicated; if tumorous or unclear lesions detected repeat CT every 9 weeks or if clinically indicated
- ◆ Clinical examination (WHO PS only) every 9 weeks and as clinically indicated
- ◆ All ongoing adverse events should be followed every 9 weeks until resolution or stabilization.

HRQoL: QLQ-C30 (v3) and the BN-20 questionnaire at month 6 after treatment start for all patients regardless of treatment arm or progression status (see chapter 10).

Patient should be followed for survival every 9 weeks until PD or one year after randomization (whatever happens first) and every 12 weeks thereafter.

6.5 Summary table

	Within 4 weeks prior to randomization ⁷	Within 2 weeks prior to randomization	During treatment		After treatment		
			On day 1 of each cycle or within 72 hours before	Every 9 weeks	End of treatment (30 days after last treatment administration)	Until PD every 9 weeks	After PD, every 9 weeks for the first year from randomization and every 12 weeks thereafter
Informed consent	♦						
Clinical examination	♦		♦		♦	♦ ⁸	
Medical history, demographics	♦						
Recording of corticosteroid dose	♦			♦		♦	
Adverse events assessment	♦		♦		♦	♦	
ECG	♦						
LVEF	♦						
Hematology ³	♦		♦		♦		
Serum chemistry ⁴	♦		♦		♦		
Pregnancy test	♦ ¹		♦ ¹		♦ ²		
Quality of life questionnaire (QLQ-C30 and BN20)	♦		♦ ⁵				
Tumor evaluation using cranial MRI		♦ ¹⁰		♦		♦ ⁹	
CT torax/abdomen		♣		♣ ⁶		♣ ⁶	
Survival						♦	♦

♦ mandatory

♣ if clinically relevant

1. Perform only in women of childbearing potential. The pregnancy test has to be done within 72h prior to randomization and also within 72 hours prior to treatment start and repeated during protocol treatment every two treatment cycles.

2. Pregnancy test must be repeated at 30 days and 3 months after last treatment dose.

3. Hematology test includes white blood cells, neutrophils, lymphocytes, platelets, hemoglobin counts.

Note for the experimental arm only: additional monitoring of hematological values should occur weekly during the first two cycles of therapy, and at least once between treatments in subsequent cycles.

4. Serum chemistry includes at least creatinine, total bilirubin, ALT, AST, ALP, CPK, albumin, LDH,

sodium, potassium, glucose, calcium. If alkaline phosphatase > 2.5 ULN, ALP hepatic isoenzyme and/or 5-nucleotidase and/or gamma glutamyltransferase (GGT) must be performed. Note: for the experimental arm only, additional monitoring of biochemical parameters (ALP, total bilirubin, CPK, and aminotransferases [AST and ALT]) should occur weekly during the first two cycles of therapy, and at least once between treatments in subsequent cycles.

5. QLQ-C30 (v3) and BN-20: at end of week 3/end of cycle 1, end of week 6/end of cycle 2, end of week 12/end of cycle 4 after treatment start, and at month 6 after treatment start regardless of treatment arm or progression status.

6. Only in patients with known tumorous or unclear lesions on prior CT

7. All evaluations performed more than 28 days prior to treatment start must be repeated

8. Only WHO PS

9. After discontinuation of protocol treatment, patients who have not progressed will still be re-evaluated every 9 weeks for the first year from randomization and every 12 weeks thereafter.

10. MRI scans acquired up to 2 years before inclusion of patients into this trial should also be submitted.

7 Criteria of evaluation

7.1 Evaluation of efficacy

Objective tumor response and time to progression will be measured according to the Macdonald response criteria (Ref. 11).

Response criteria are essentially based on a set of measurable lesions identified at baseline as target lesions, and – together with other lesions that are denoted as non-target lesions – followed until disease progression.

The following paragraphs are a quick reference to the Macdonald response criteria.

7.1.1 Measurability of tumor lesions at baseline

7.1.1.1 General method of response assessment

Objective response to treatment is based on assessment at the treating site, following the provided imaging guidelines.

Response to treatment is assessed on the basis of a set of target lesion(s) chosen before the first treatment administration (the complete list of target lesions must be reported on the initial measurement form before the start of treatment). These lesions must initially be measured in their two perpendicular dimensions, and these measurements must be repeated at each evaluation of the disease by the same method. Response evaluation for this protocol is based on neuro-radiological imaging (MRI).

The contrast enhancing area will be considered as the basis for the tumor size assessment. Tumor size is defined as the product of the two largest perpendicular diameters. The initial comparison must be done against the baseline scan. In initially responding ($\geq 50\%$ reductions in cross-sectional areas) or stabilized ($<50\%$ reduction and $< 25\%$ increase in cross-sectional areas) patients, new scans must be compared to the nadir, i.e. the scan showing the maximum response (= minimum tumor size) during or after treatment. In assessing response, changes on T1-Gd+ images must be taken into consideration.

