- ◆ No known MRI or CT, including contrast media, contraindications
- ◆ Absence of any psychological, familial, sociological or geographical condition potentially hampering compliance with the study protocol and follow-up schedule; those conditions should be discussed with the patient before registration in the trial
- ◆ Before patient randomization, written informed consent must be given according to ICH/GCP, and national/local regulations.

Important note: All eligibility criteria must be adhered to, in case of deviation discussion with Headquarters and study coordinator is mandatory.

4 Trial Design

This is a randomized open label multicenter comparative phase II trial. The Korn design (Ref. 10) will be applied (for detailed statistical considerations see chapter 8).

[figure not shown]
Patients will be randomized at the EORTC headquarters after verification of the eligibility criteria (see chapter 3) to receive one of the following:

- ◆ Arm 1 (treatment): Trabectedin delivered as a 24-hour infusion every 3 weeks (day 1 of each 21-day cycle) at a starting dose of 1.5 mg/m² body surface area (BSA), until one of the treatment withdrawal criteria has been met.
- ◆ Arm 2 (control): Local standard of care.

For the trabectedin arm one cycle will be defined as 3 weeks.

For the control arm one cycle will be defined according to the treatment schedule of the chosen drug.

Disease will be assessed by the Macdonald response criteria (see chapter 7).

5 Therapeutic regimens, expected toxicity, dose modifications

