Baseline tumor evaluations performed more than 28 days prior to treatment start must be repeated.

- ◆ Tumor evaluation (no more than 2 weeks prior to randomization): assessed by standard methodology using cranial MRI. CT thorax/abdomen should be performed if clinically indicated. The same method should be used for repeated measurements throughout the study.

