7.1.1.2 Definition

- ◆ **Measurable disease** - the presence of at least one measurable lesion. If the measurable disease is restricted to a solitary lesion, its neoplastic nature should be confirmed by cytology/histology.
- ◆ **Measurable lesions** - *tumor lesions* that can be accurately measured in at least one dimension (longest diameter to be recorded) as ≥ 10 mm with MRI scan. Bone lesions are considered measurable only if assessed by CT scan and have an identifiable soft tissue component that meets these requirements (soft tissue component > 10 mm by CT scan). *Malignant lymph nodes* must be ≥ 15 mm in the short axis to be considered measurable; only the short axis will be measured and followed. All tumor measurements must be recorded in millimeters (or decimal fractions of centimeters). Tumor lesions situated in a previously irradiated area, or in an area subjected to other loco-regional therapy, are usually not considered measurable unless there has been demonstrated progression in the lesion.
- ◆ **Non-measurable lesions** - All other lesions (or sites of disease), including small lesions are considered non-measurable disease. Bone lesions without a measurable soft tissue component and leptomeningeal disease are non-measurable. Nodes that have a short axis <10 mm at baseline are considered non-pathological and should not be recorded or followed.

Target Lesions. Only the following lesions are eligible as target lesions:

- ◆ MRI contrast enhancing lesions with two perpendicular diameters of 10 mm or more visible on 2 or more axial slices which are 5 mm apart.
- ◆ Target lesion(s) must be measurable in two perpendicular diameters.

In most patients, only one lesion will be present. In case of multifocal disease, a minimum of 2 lesions and maximum of 5 largest enlarging lesions will be chosen as target and the sum of the products of the perpendicular diameters will be determined. All other lesions than target lesions, if applicable, are assessed according to the same schedule. They are only taken into account in two situations:

- ◆ If one of them clearly progresses, the overall response to therapy will be evaluated as "progression", independent of the response of target lesions
- ◆ All lesions must have completely disappeared to report a "complete response".

Adequate investigations must be carried out at each evaluation of the disease to detect eventual new lesions. If any new lesion is found, the response will be evaluated as "progression".

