14.1 Case report forms and schedule for completion

Data will be reported on the forms specifically designed by the EORTC Headquarters for this study. Forms should be electronically sent to the EORTC Headquarters through the VISTA/RDC (Remote Data Capture) system with the exception of the quality of life form, the SAE form and the Pregnancy notification form which are paper CRFs.

Copies of the Quality of Life should be sent directly to the EORTC Headquarters by one of the following means:

By fax, to the attention of "BTG" Data manager: [name]

By scanning and e-mailing the forms to [contact] (see guidelines for completion of case report forms)

By regular mail to the EORTC Headquarters:

("BTG" Data Manager)
EORTC Headquarters
[name]
[name]
België - Belgique

SERIOUS ADVERSE EVENTS AND PREGNANCY NOTIFICATION FORMS SHOULD BE IMMEDIATELY REPORTED ACCORDING TO THE PROCEDURE DETAILED IN THIS PROTOCOL (see chapter 15 on Reporting Serious Adverse Events).

A. Before the treatment starts:

- ♦ The patient must be randomized in the trial by INTERNET or in case of problems by phone.

The electronic CRFs to be completed for a patient are available on the VISTA/RDC website one hour after the randomization on <http://rdc.eortc.be/> or on <http://www.eortc.org> in the investigator area.

The paper CRFs will be made available to the institution at the time the institution is authorized.

B. During/after treatment

The list of forms to be completed for this study and their submission schedule are available on the VISTA/RDC website and are also described in the "guidelines for completion of case report forms" that are provided to each participating investigator.

ALL Forms must be electronically approved and sent by the responsible investigator or one of his/her authorized staff members with the exception of the paper quality of life form (no signature needed).

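### Target lesions may be chosen and recorded after open-label randomization, so the site-read baseline for PFS and response can be set with the arm known; the size of any bias cannot be derived

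*Combined protocol and SAP*

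**What the plan says.** The trial design (chapter 4) is stated plainly: "This is a randomized open label multicenter comparative phase II trial". Section 7.1.1.1 places the reading at the site: "Objective response to treatment is based on assessment at the treating site, following the provided imaging guidelines". The same section bases response on "a set of target lesion(s) chosen before the first treatment administration" and adds that "the complete list of target lesions must be reported on the initial measurement form before the start of treatment". Both deadlines refer to treatment. No section of the supplied documents asks for the list before randomization.

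The opening of chapter 6 sets the gap between randomization and treatment: "A maximum delay of 21 days is accepted". Section 14.1 says: "The electronic CRFs to be completed for a patient are available on the VISTA/RDC website one hour after the randomization".

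For multifocal disease, section 7.1.1.2 says that "a minimum of 2 lesions and maximum of 5 largest enlarging lesions will be chosen as target". It also says that most patients will have a single lesion.

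Section 6.2 requires the baseline cranial MRI within two weeks before randomization. It also requires any baseline tumor evaluation more than 28 days old at treatment start to be repeated. Section 7.1.1.2 repeats the four-week limit and wants baseline as near to treatment start as possible.

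**The concern.** Partial response is a percentage fall from the baseline sum of products. Progression in target lesions is a rise of at least 25% over the smallest sum on study, with the baseline scan included (section 7.1.2). The baseline list and diameters therefore enter primary PFS (section 7.1.3) and the response endpoints.

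In an open-label trial, anything settled after allocation by someone who knows the arm can differ between arms for reasons unrelated to the drug. Here three things may still be open when the arm is revealed: how many lesions are targets in multifocal disease, which ones they are, and the slice and diameters recorded. A baseline read generously in one arm delays measured progression in that arm. This need not be deliberate.

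**Working it through.** **1. Can selection follow allocation?** The deadline for choosing and recording is treatment start (7.1.1.1). Treatment may start up to 21 days after randomization (chapter 6). The allocation is not masked (chapter 4) and the reader is at the site (7.1.1.1). So selection with the arm known is permitted for up to 21 days.

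**2. When is the form filled in?** Section 14.1 lists the paper forms as quality of life, SAE and pregnancy notification. The initial measurement form is not among them, so it is presumably electronic and opens one hour after randomization. This is an inference. It concerns entry on the form, not when lesions were picked in the source. Step 1 does not depend on it.

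**3. Can the baseline scan itself follow allocation?** Inputs: MRI up to 14 days before randomization (6.2), treatment up to 21 days after it (chapter 6), repeat if more than 28 days old (6.2).
- Oldest eligible MRI at treatment start: 14 + 21 = 35 days, which exceeds 28.
- With a 14-day-old MRI, a start later than day 28 − 14 = 14 forces a new baseline scan after allocation.
- An MRI no more than 28 − 21 = 7 days old at randomization never triggers the rule within the permitted delay.

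**4. What could a baseline reading error do?** Suppose that baseline diameters are read high by a fraction e and later scans are read correctly. The values of e are assumed.
- True area growth needed for a measured 25% rise: 1.25(1 + e)² − 1.
- Time-to-threshold ratio under steady exponential growth: ln[1.25(1 + e)²] / ln(1.25).

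| e | Growth needed | Time ratio |
|---|---|---|
| 2% | 30% | 1.18 |
| 5% | 38% | 1.44 |
| 10% | 51% | 1.85 |

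These are ceilings. If true growth by the first follow-up scan is below (1 + e)² − 1 (4%, 10% and 21% respectively), that scan gives the smaller sum and becomes the reference. If the same reader overreads every scan by the same fraction, the error cancels.

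**5. What would a shift in the hazard ratio mean for the test?** First the plan's own figure. HR = ln(0.35)/ln(0.15) = 0.553. With one-sided alpha 10%, 85% power and 2:1 allocation, Schoenfeld's formula gives (1.2816 + 1.0364)² / [(2/9)(ln 0.553)²] = 69.06, so 70 events, close to the stated 72. Power at 72 events is 86.1%.

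If arm-aware baseline setting moved the null HR from 1 to b, the one-sided type I error at 72 events would be 1 − Φ(1.2816 − √(72 × 2/9) × |ln b|), where √(72 × 2/9) = 4.

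| b (assumed) | Type I error |
|---|---|
| 1.00 | 10% |
| 0.97 | 12.3% |
| 0.95 | 14.1% |
| 0.90 | 19.5% |
| 0.85 | 26.4% |

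The documents give no basis for any value of b other than 1, nor for the direction of a shift.

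**The case against.** The case that this matters little is strong on size.

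- **Little to choose.** Most patients have one lesion. In the rest, the rule points to the largest lesions that are growing, and size is the product of the two longest perpendicular diameters. This stands, although the number of targets is left between 2 and 5 and the measurement is made in every patient.
- **Self-correction.** The smallest-measurement reference limits an inflated baseline, and section 6.3.1 asks for the same method and, if possible, the same person. This stands; it is why step 4 gives ceilings.
- **Other routes to progression.** New lesions, clear non-target progression and clinical worsening do not use the target sum. They dilute the effect.
- **Independent review.** Section 16.6.1.4 plans a central review masked to arm and to the site's reading, and section 16.5 has responses reviewed by independent experts. Both can expose a problem. But the central review is retrospective and confirmatory (11.2), section 8.2.3.1 does not name it as the source of PFS, and section 8.2.4 pre-plans no sensitivity analysis.
- **Some measurement already precedes randomization.** Disease of 10 x 10 mm is an entry criterion, and chapter 13 asks for actual eligibility values where applicable. That shows one qualifying lesion; it fixes neither the list nor the baseline sum.
- **Documents not supplied.** The imaging guidelines or the Central Review Charter may lock the list earlier. If so, 7.1.1.1 should be aligned with them.

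Three stronger readings are tempting and are not supported. A reader might infer that sites can turn progression into stable disease by choosing lesions: with five equal lesions, one growing 60%, the sum rises 60/5 = 12% with five targets and 60/2 = 30% with two. But section 7.1.1.2 defines non-target lesions as those failing the target criteria, so five qualifying, enlarging lesions would ordinarily all be targets. Knowing the arm also does not reveal which lesion will grow, so the example shows variability, not bias toward an arm. A reader might infer that the whole baseline could simply be frozen before randomization; the 28-day repeat rule prevents that for some patients. And a reader might take the tables in steps 4 and 5 as estimates of bias; they rest on assumed inputs.

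**Conclusion.** The point holds as a gap in timing. Section 7.1.1.1 lets the site-read baseline reference be set up to 21 days after open-label randomization, and nothing in the supplied documents closes that window. For some patients the baseline scan itself must be repeated after allocation. The documents do not show that baselines will be set differently by arm, and the size and direction of any bias in PFS or response cannot be derived from them. The conclusion assumes that the unseen imaging documents contain no earlier lock. It leaves the 72 events and 86 patients unchanged. This is a cheap improvement worth making, not a flaw that undermines the primary analysis.

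**What to change.** In section 7.1.1.1, require the target lesions and their baseline diameters to be selected, measured and dated before randomization, on the MRI that section 6.2 already requires. They can be recorded in the source or entered on the randomization checklist with the eligibility values.

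Add a rule for repeat scans: where section 6.2 or the four-week limit in section 7.1.1.2 forces a new baseline scan after randomization, the same pre-specified lesions are re-measured, none is re-selected, and both sets of measurements are kept.

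The cost is a short text change, one checklist item and a slightly earlier site reading. No extra scan, reader or patient is needed. Two exposures remain: later scans are still read at the site with the arm known, and in repeat-scan patients the baseline diameters are still measured after allocation.
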